7.4.2 Efficacy Analysis of the Exploratory Endpoints

Definitions and analysis methods for the exploratory endpoints are introduced in this section.

Tables will display results by analysis visit window as defined in Section 7.2.5.

Migraine-Specific Quality of Life Questionnaire (MSQoLQ) V2.1

This questionnaire has 14 items and 3 domains (Restrictive Role Function, Preventive Role Function, and Emotional Function), among which Restrictive Role Function consists of 7 items, Preventive Role Function consists of 4 items, and Emotional Function consists of 3 items. A 6-point scale is adopted for the answer options to each item, with 1 indicating the quality of life is not damaged ("Never") and 6 indicating maximum damage ("All the time"). First, individual item scores are recoded as $\{7 - \text{original item score}\}$. Next, the sum of the questionnaire results of all recoded items in each domain will be calculated and used as the raw score. If in a particular domain, the questionnaire results of less than or equal to half of the items are missing (e.g., the questionnaire results of ≤ 3 Restrictive Role Function items, ≤ 2 Preventive Role Function items are missing, or ≤ 1 Emotional Function item are missing). The raw score of the domain will be imputed as the mean of the questionnaire results of non-missing items. If in a particular domain, the questionnaire results of more than half of the items are missing, the raw score of the domain will be regarded as missing. And then, the raw score of each domain will be transformed into a score in the 0-100 scale. Each domain will be analyzed based on the transformed raw score.

The transforming rules are shown in the figure below:

Domain	Raw score transforming rule
Restrictive Role Function	$(\text{Raw score} - 7) * 100/35$
Preventive Role Function	$(\text{Raw score} - 4) * 100/20$
Emotional Function	$(\text{Raw score} - 3) * 100/15$

The transformed raw score and change from baseline for each domain will be presented by visit

and domain, with n, mean, SD, maximum, minimum, median, and 95% CI as described in Section 7.1.

A listing of original item scores and transformed scores for each domain from the MSQoL questionnaire will be provided.

Migraine Preference of Medication Questionnaire (PoM)

PoM is a 5-item rating scale used to record participants' perception of whether the study drug they are taking is more beneficial in treating their pain compared with prior medication. The statistical analysis will be based on 3 categories, as shown in the figure below:

Item	Category
I feel much better, and I prefer this drug	Preference for study drug
Slightly better than the prior medication	Preference for study drug
Basically the same as the prior medication	No preference
Slightly worse than the prior medication	Preference for prior medication
I feel much worse, and I prefer my prior medication	Preference for prior medication

The number and percentage of participants in each category will be summarized by visit. The calculation of percentage will be based on participants with PoM data by visit, and the two-sided exact Clopper-Pearson 95% CI will be calculated as described in Section 7.1.

A listing of Preference of Medication (PoM)- will be provided.

Satisfaction with Medication Questionnaire (SM)

The SM questionnaire is a 7-item rating scale used to record whether participants are satisfied with their headache medication. The number and percentage of participants in each category will be summarized by visit. The calculation of percentage will be based on participants with SM data by visit, and the two-sided exact Clopper-Pearson 95% CI will be calculated as described in Section 7.1.

A ~~listing~~ listing of Satisfaction with Medication (SM) Survey will be provided.

Migraine Disability Assessment Questionnaire (MIDAS)

The MIDAS questionnaire is a retrospective participant self-report scale consisting of 5 questions, which is used to measure disability related to headache, such as time lost due to headache caused by paid work or school, housework, and non-working activities. The value and change from baseline in the total score will be presented by visit, with n, mean, SD, maximum, minimum, median and 95% CI as described in Section 7.1.

The total score is calculated as the sum of item scores to all 5 questions.

A listing of individual item score, and the calculated total score will be provided.

Clinical Global Impression-change (CGI-c) scale

The CGI-c scale is a 7-item observer-rated scale used to assess the global improvement in

participants. The number and percentage of participants in each category will be summarized by visit. The calculation of percentage will be based on participants with CGI-c data by visit, and the two-sided exact Clopper-Pearson 95% CI will be calculated.

A listing of individual item responses will be provided.

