### **Overall Design:**

This is a multicenter, open-label study to assess the safety and tolerability of long-term use of 75 mg rimegepant ODT, dosed as PRN, taken up to one tablet per calendar day, in Chinese participants with migraine.

The Screening phase includes a Screening Visit and a 30-day Observation Period (OP). For participants to be eligible for the study, they must have 6-18 migraine attacks of moderate to severe intensity per month in the 3 months prior to the Screening Visit.

Upon the completion of the Screening Visit, participants will be provided an electronic diary (eDiary) to document each day of the 30-day Observation Period if a migraine occurs, the intensity of each migraine attack and if the migraine is treated. Participants will record the standard of care migraine treatment received on a personal device APP (BYOD, Bring Your Own Device). After the completion of the 30-day OP, participants will return to the clinic for the Baseline Visit. At the Baseline Visit, eligibility for the continuing participation in the study will be assessed before study medication is dispensed. Participants need have at least 6 migraine days during the 30-day OP to be eligible and women of childbearing potential (WOCBP) must have a negative pregnancy test result prior to dispensing study drug. After the investigator reviews the results of the baseline laboratory assessments and determines the participant's eligibility, the site staff will inform the participant whether or not he/she is eligible to start dosing in the Long-Term Treatment Phase (LTT). The eligible participants will be instructed that they can take a maximum of one tablet of rimegepant per calendar day during the 52-week Long-Term Treatment Phase at the onset of a migraine (of mild to severe intensity).

Participants are required to record their migraine occurrence and severity via eDiary, and all study medication dose and standard of care migraine treatment taken via BYOD. Participants will also use BYOD to complete the Preference of Medication (PoM) questionnaire and the Satisfaction with Medication (SM) questionnaire at specified study visits.

At select study visits, participants will complete or will be administered the Migraine-specified Quality-of-Life Questionnaire v 2.1 (MQoLQ), the Migraine Disability Assessment (MIDAS), and Clinical Global Impression-change (CGI-c) scale in the paper scales provided by study site.

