### **10.5.4. Exploratory Endpoints**

For MSQoLQ and MIDAS rating scales, total and/or domain scores, and changes from baseline in the total and/or domain scores will be descriptively summarized by visit with two-sided 95% CIs based on normal distribution.

For PoM, SM, and CG-c rating scales, number and percentage of participants in each category will be summarized by visit with two-sided exact Clopper-Pearson 95% CIs for the percentage of participants in each category.

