4.3 Exploratory Endpoints

- Change from baseline in results assessed with the 14-item MSQoLQ version 2.1 following treatment with 75 mg rimegepant ODT.
- Percentage of participants in each of 3 preference categories of the assessment with Migraine PoM for migraine following treatment with 75 mg rimegepant ODT.
- Percentage of participants in each of 7 satisfaction categories of the SM survey following treatment with 75 mg rimegepant ODT.
- Change from baseline in total score of the MIDAS following treatment with 75 mg rimegepant ODT.
- Percentage of participants in each of 7 categories of the CGI-c scale after treatment with 75 mg rimegepant ODT.

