5 STUDY HYPOTHESIS

The statistical analysis is mainly descriptive, and no formal hypothesis testing will be performed.

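### The SAP's MSQoLQ missing-item rule feeds an item mean into a transform built for the item sum, so the affected domain scores come out far too low

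*SAP*

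**What the plan says.** SAP Section 7.4.2 scores the 14-item MSQoLQ in a fixed order.

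1. Each item, answered on a 1 to 6 scale, is recoded as 7 minus the answer.
2. For each domain, "the sum of the questionnaire results of all recoded items in each domain will be calculated and used as the raw score". The domains are Restrictive (7 items), Preventive (4) and Emotional (3).
3. If no more than half of a domain's items are missing (up to 3, 2 and 1 items respectively): "The raw score of the domain will be imputed as the mean of the questionnaire results of non-missing items". If more than half are missing, the domain score is missing.
4. After that, "the raw score of each domain will be transformed into a score in the 0-100 scale", using (raw - 7) × 100/35, (raw - 4) × 100/20 and (raw - 3) × 100/15.

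On reporting, the same section says: "The transformed raw score and change from baseline for each domain will be presented by visit". The summary includes mean, SD, median, minimum, maximum and 95% CI. The endpoint in SAP Section 4.3 is "Change from baseline in results assessed with the 14-item MSQoLQ version 2.1 following treatment with 75 mg rimegepant ODT". Protocol Section 10.5.4 says only that "changes from baseline in the total and/or domain scores will be descriptively summarized by visit with two-sided 95% CIs" and gives no item-level scoring rule.

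**The concern.** Step 3 assigns the mean to the domain's raw score, not to the missing item. Step 4 then subtracts 7, 4 or 3 and divides by 35, 20 or 15, constants that make sense only for a sum. No step in between converts the mean back to the sum scale, and no other section of either document does so.

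The endpoint is a change from baseline, so the damage depends on where the gap falls. A gap at a later visit pulls the change down and can reverse its sign. A gap at baseline inflates the improvement. Gaps in the same domain at both visits shrink it. The questionnaire is scheduled at baseline, Weeks 12, 28 and 40, and Week 52 or early termination. The protocol synopsis (Overall Design) puts it on paper, with the words "scale in the paper scales provided by study site", so skipped items are possible.

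**Working it through.** **Inputs, all from SAP Section 7.4.2.** Items per domain k = 7, 4, 3. Recoded item range 1 to 6. Transform T(raw) = (raw - k) × 100/d with d = 35, 20, 15, that is d = 5k.

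**The plan's own figure, complete data.** The raw sums run 7-42, 4-24 and 3-18. T(7) = T(4) = T(3) = 0 in their respective domains, and (42 - 7) × 100/35 = (24 - 4) × 100/20 = (18 - 3) × 100/15 = 100. The stated 0-100 scale is reproduced, so the transforms are correct for the sum.

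**Partly missing domain.** Let m be the mean of the answered recoded items.

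- As written: w(m) = (m - k) × 100/d.
- With each missing item filled by m and then summed: c(m) = (km - k) × 100/d = 20(m - 1), which is 0 to 100 in every domain.
- Error: w - c = -(k - 1)m × 100/d, that is -17.14m, -15m and -13.33m.

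| | Restrictive | Preventive | Emotional |
|---|---|---|---|
| w at m = 1 (c = 0) | -17.1 | -15.0 | -13.3 |
| w at m = 4 (c = 60) | -8.6 | 0.0 | 6.7 |
| w at m = 6 (c = 100) | -2.9 | 10.0 | 20.0 |
| Error at m = 4 | -68.6 | -60.0 | -53.3 |

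The error is negative for every permitted number of missing items and every set of answers. The as-written score falls inside 0-100 for Preventive when m ≥ 4 and for Emotional when m ≥ 3.

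**Change from baseline.** Illustrative item means are 3.5 at baseline and 4.5 later. The true change is c(4.5) - c(3.5) = 70 - 50 = +20.

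| Where the gap is | Restrictive | Preventive | Emotional |
|---|---|---|---|
| Later visit only: w(4.5) - 50 | -57.1 | -47.5 | -40.0 |
| Baseline only: 70 - w(3.5) | +80.0 | +72.5 | +66.7 |
| Both visits: w(4.5) - w(3.5) | +2.9 | +5.0 | +6.7 |

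With gaps at both visits the true change is divided by k, that is by 7, 4 or 3.

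**Group level, by assumption only.** Take Restrictive, n = 240 and the same item means. One later-visit gap shifts the mean change by -77.1/240 = -0.32, and one baseline gap by +60.0/240 = +0.25. Five later-visit gaps shift it by 5 × (-77.1)/240 = -1.6. The SD of change becomes √(s² + q(1 - q) × 77.1²) with q = 5/240:

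- s = 15 gives 18.6 (+24%)
- s = 20 gives 22.8 (+14%)
- s = 25 gives 27.3 (+9%)

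**The case against.** The strongest reply is that this is a slip of wording. The paragraph defines the raw score as a sum and promises a 0-100 scale. The missing-item text is visibly broken, because its condition ends in a full stop before the consequence begins. The intent was probably to fill each missing item with the mean and then sum. The documents do not show how the score was programmed. That is fair about intent, but it does not repair the rule. A programmer who follows it gets scores outside the SAP's own scale, and one who corrects it departs from the SAP without saying so.

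Second, the missing-item sentence does not repeat that the items are recoded. Recoding comes first, so recoded items are the natural reading. If the original answers (mean 7 - m) were averaged instead, Restrictive would still always be negative and too low. Preventive and Emotional errors would be 35 - 25m and 46.7 - 26.7m, so at m = 1 (worst impairment) those scores would be 10 and 20 points too high. The statement that every affected score is too low therefore rests on the recoded reading. The rule fails on either.

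Third, the error could be noticed. The tables show minimum and maximum, and the listing sets item scores beside transformed scores, so a negative Restrictive minimum would stand out. That is true for Restrictive. In-range Preventive and Emotional errors would need someone to check the listing.

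Fourth, the group figures are hypothetical, and n = 240 ignores dropout. With the plan's 12%, 240 × 0.88 ≈ 211 participants remain, and one later Restrictive gap moves the mean by -77.1/211 = -0.37. The figures are illustrations only.

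Last, the endpoint is exploratory. SAP Section 5 states: "The statistical analysis is mainly descriptive, and no formal hypothesis testing will be performed". This limits the consequence and is accepted.

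**Conclusion.** The rule is wrong as written and should be corrected. With the mean taken over recoded items, each domain score computed under it is too low by 17.14, 15 or 13.33 points per unit of item mean. Over item means 1 to 6 that is 17.1 to 102.9 points in Restrictive, 15 to 90 in Preventive and 13.3 to 80 in Emotional.

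The per-score errors follow from the SAP's constants alone. The change-from-baseline examples also assume item means of 3.5 and 4.5. The group effects further assume the number of gaps, the sample size and the SD. How much the reported means would move cannot be determined from the documents.

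The scope is narrow. Only a domain with some, but no more than half, of its items missing is affected. Complete domains are scored correctly. No primary or secondary result depends on this score.

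**What to change.** Replace the missing-item sentence in SAP Section 7.4.2 with:

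> If half or fewer of the items in a domain are missing, each missing item is imputed with the mean of the non-missing recoded items in that domain, and the raw score is the sum of observed and imputed items (that mean multiplied by the number of items in the domain).

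Keep the three transforms and the rule for domains with more than half their items missing. A Restrictive item mean of 4 then gives (28 - 7) × 100/35 = 60, and every domain stays within 0-100. Naming the recoded items also settles which answers are averaged.

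The cost is one sentence in the SAP and, if the scoring program follows the present text, about one line of code. Data collection and the other analyses do not change, and there is no downside.

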7.5 Safety Analyses

Safety analyses during the pre-treatment, treatment safety analysis periods will be summarized based on the SS. Safety analyses for follow-up safety period will be summarized based on FUSS.

7.5.1 Drug Exposure

Drug administration data collected via CRF will be used to summarize drug exposure as follows:

- Time in the OP (weeks) = (OP end date – OP start date + 1)/7
- Time in the LTT period (weeks) = (LT^T analysis period end date – LT^T analysis period start date + 1)/7
- Time on rimegepant exposure (weeks) = (study drug end date – study drug start date + 1)/7
- Cumulative administered rimegepant dose (tablets) = sum of doses administered on the drug management page of CRF.
- Average administered rimegepant dose during the LTT period (tablets per month) = 4 (weeks)*cumulative administered dose (tablets) / Time in the LTT period (weeks) if time in the LTT period \geq 2 weeks; = cumulative administered dose if time in the LTT period $<$ 2 weeks.

In the above drug exposure summary, descriptive statistics of n, mean, standard deviation, median, 25th and 75th percentiles, minimum and maximum will be presented.

- For the average rimegepant exposure during the LTT period (tablets per month), the number and percentage of participants will be summarized by < 2, \geq 2 to < 8, \geq 8 < 14, < 14 and \geq 14 tablets per month.
- The number and percentage of participants taking > 1 tablet per day (i.e., actual dose of “other”). It will be calculated based on the study drug administration CRF.

In addition, rimegepant exposure during the LTT period will be summarized by the average Rimegepant exposure categories and total for each month (i.e., 4-week interval) as defined in [Table 2](#). The rimegepant exposure (tablets) for each month will be determined as follows:

- rimegepant exposure (tablets) for Month X = sum of doses administered on the drug management page of CRF within the Month X window, where X=1, 2, 3, 4, 5, 6, 7, 8, 9, 10, 11, 12.

- Rimegepant exposure (tablets) for Month 13 = sum of doses administered on the drug management page of CRF within the Month 13 window if exposure \leq 28 days; = sum of doses administered on the drug management page of CRF within the Month 13 window *28/exposure days if exposure $>$ 28 days.

Participant's exposure to the study drug will be listed in detail.

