**Table 1. Assessment Schedule**

Procedure	Screening Visit	Observational Period (30 days, ±2 days)	Baseline Visit (Day 1)	Phone visit to confirm eligibility based on Clinical Laboratory Findings	Weeks 4, 8, 12 (all visits ±3 days)	Weeks 16, 28, 40, 52 (or Early Termination) (all visits ±7 days)	Phone visits Weeks 20, 24, 32, 36, 44, 48(all visits ±7 days)	Follow-up Safety Visit (14 days after EOT visit ±2 days)
------------------	------------------------	--	---	---	--	---	--	---

6. Upon completion of the Baseline Visit, WOCBP will be provided with urinary pregnancy test kits so that participants can test at home if necessary. When WOCBP participants cannot confirm pregnancy status, a urine pregnancy test must be completed at home before taking study drugs.
7. All SAEs and AEs must be reported by the participant after signing the informed consent.
8. To be determined to be eligible prior to dispensing study drug, participants must have a history of migraine attacks for at least 6 days during the 30-day Observation Period and WOCBP must have a negative pregnancy test result prior to dispensing study drug. Week 4, 8, 2: dispensing 3 wallets to the participant on the monthly visits. Week 16, 28, 40: according to the participant's need to dispense wallets, maximum is 7 wallets. The study drug will not dispense at Week 52 as that is EOT.
9. Participants will be instructed that they can take the study medication at the time of their migraine attack (mild, moderate, or severe), up to 1 tablet per day. The participant must record in the BYOD the study drug taken for each tablet.
10. If a participant lacks 6 or more eDiary reports per month for 2 months (continuous or non-continuous), the participant's continued participation in the study should be terminated due to lack of compliance.
11. The eDiary will be dispensed at the Screening Visit after the participant has completed all screening procedures. Participants will be trained in the use of the eDiary. Participants will use eDiary daily during the observation and Long-Term Treatment Periods to record migraine attacks, migraine severity, and whether they receive migraine treatment.

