## 5.5. Prophylactic and Standard of Care Migraine Medications

Participants using prophylactic migraine medications are permitted to remain on therapy if the dose has been stable for at least 2 months prior to the Baseline Visit and this dose is not expected to change during the study. Participants who previously discontinued prophylactic migraine medication must have done so at least 5 half-lives of the prophylactic medication prior to the Screening Visit.

Participants may need to take previously prescribed standard of care medications: aspirin, ibuprofen, acetaminophen (including Excedrin®Migraine) up to 1000 mg/day for a maximum of 2 consecutive days at a time, naproxen (or any other type of non-steroidal anti-inflammatory [NSAID]), antiemetics (eg, metoclopramide or promethazine), or muscle relaxants, which are used during the study (Observation Period and Long-Term Treatment Phase) for the standard of care treatment of migraine.

Use of triptans by participants without a contraindication to their use is allowed during the Observation Phase but must be discontinued at the Baseline Visit. As described above, use of triptans is prohibited during the Long-Term Treatment Phase. With the exception of triptans described in this section, participants are allowed to take standard treatment for migraine during the study, if needed, but are required to meet dose restrictions if taking acetaminophen (no more than 1000 mg/day at a time for 2 consecutive days).

If a participant takes a tablet of study drug and experiences a migraine later that day, the participant can take standard of care medications for migraine (as described in this section above) after taking the study drug that day. Participants are not allowed to take more than 1 tablet of the study medication per calendar day.

Use of standard of care medications during Observation Period and Long-Term Treatment Phase, will be recorded by the participant via BYOD and reported to the site.

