### **7.4. Treatment Compliance**

Study drug will be dispensed by the responsible study personnel. Drug accountability and compliance check results should be documented in the participant's study records.

Participants should be instructed on the importance of taking the study drug as directed when a migraine attack occurs (mild, moderate, or severe). At site visits, the responsible study personnel will review the use of study drug recorded in the BYOD and the returned study drug to assess treatment compliance. Dose discrepancies reported by BYOD, review of study drug, and information provided by the participant must be documented in the original medical record. Data in BYOD for incorrect or missing doses and migraine headaches will be corrected by the Data Clarification Record or Study Drug Reconciliation Form. The investigator shall inform the participants participating in the study that if it is confirmed that the participants are lack of compliance, the participants will be terminated to continue to participate in the study. During monthly study visits, if a participant's BYOD records a lack of compliance, the study staff should contact the participant and document this contact in the original medical record to identify potential participant loss to follow-up as early as possible.

Investigators should monitor participants for possible abuse of the study drug (participants taking the study drug for non-therapeutic purposes, such as for elevated or excited mental effects). The investigator should also assess study drug accountability discrepancies (e.g., missed study drug, lost study drug, overuse of study drug). In the event of a study drug accountability discrepancy, the investigator should obtain additional information and explanation from the participant.

Potential cases of study drug abuse or overdose (including failure to return study drug for participants who fail to take the study drug as instructed or discontinue treatment) should be recorded in original medical records, and AEs or SAEs should be reported as appropriate. Protocol deviations should be documented in the event of dose errors (e.g., taking more than 1 tablet on a calendar day).

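### SAP 7.5.1 counts participants taking more than one tablet per day by a CRF dose category, although the protocol limit is a total over a calendar day

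*SAP*

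**What the plan says.** SAP 7.5.1 (Drug Exposure) opens with its data source: "Drug administration data collected via CRF will be used to summarize drug exposure as follows". Among the summaries it lists "The number and percentage of participants taking > 1 tablet per day (i.e., actual dose of" *other*), and adds "It will be calculated based on the study drug administration CRF". The abbreviation *i.e.* makes the dose category the definition of the count, not an example of it. The section ends by stating that each participant's "exposure to the study drug will be listed in detail".

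The protocol sets the limit by calendar day. Section 5.5 says "Participants are not allowed to take more than 1 tablet of the study medication per calendar day", and Section 7.4 says "Protocol deviations should be documented in the event of dose errors (e.g., taking more than 1 tablet on a calendar day").

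On recording, footnote 9 of the protocol's Table 1 says "The participant must record in the BYOD the study drug taken for each tablet". Section 7.4 then provides for reconciliation: "Data in BYOD for incorrect or missing doses and migraine headaches will be corrected by the Data Clarification Record or Study Drug Reconciliation Form".

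**The concern.** The limit is a sum over a day, while the SAP rule looks at the dose category on a CRF record. The two agree only if each record already holds the day's total and *other* is used only for totals above one tablet. The SAP states neither condition.

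The case that could slip through is foreseeable. Protocol 5.5 itself considers a participant who takes a tablet and has a further migraine later the same day. A participant who then took a second tablet would have two intakes hours apart, each of the standard amount. On a form with one row per intake, neither row would be *other*.

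At stake is the accuracy of one reported number and percentage in a 52-week as-needed safety study. The count could be too low because same-day pairs are missed, or too high because *other* takes in entries that are not above one tablet.

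**Working it through.** The documents give no expected number or rate for this count, so there is no planned figure to reproduce. The check compares the stated rule with the limit it is meant to monitor.

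**Step 1. The two rules.**
- SAP rule: flag a participant who has any record with actual dose = *other*.
- Calendar-day rule: for each participant and date, S = sum of tablets over all records on that date. Flag a participant who has any date with S > 1.

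**Step 2. Four invented participants, CRF with one row per intake.**

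| Participant | Records | SAP rule | S by date | Calendar-day rule |
|---|---|---|---|---|
| A | two 1-tablet rows, same date | not flagged | 1 + 1 = 2 | flagged |
| B | one *other* row, 2 tablets | flagged | 2 | flagged |
| C | one *other* row, 0.5 tablet | flagged | 0.5 | not flagged |
| D | one 1-tablet row on each of two dates | not flagged | 1 and 1 | not flagged |

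The SAP rule flags B and C, and the calendar-day rule flags A and B. Both totals are 2, so the reported count alone would not show that the rules picked different people.

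**Step 3. The same participants, CRF with one row per day.** A's day would be a single row of 2 tablets, presumably entered as *other*, and the SAP rule would count it. C would still be flagged wrongly unless *other* is restricted to more than one tablet. The calendar-day rule again flags A and B, so it gives the right answer under both layouts.

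**Step 4. Whether the data allow a sum by date.** SAP 7.5.1 sums CRF doses within 28-day windows, and SAP 8.1 uses CRF drug administration data to identify individual migraine days. The records must therefore carry dates.

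**Step 5. Illustration of scale, on assumed inputs only.** Assume 8 tablets per 28 days, a full 52 weeks, one-row-per-intake records, and the same independent chance p of a second tablet on each dosing day. None of these is given in the documents. The 240 participants come from protocol 10.2.
- Dosing days: 52/4 = 13 intervals; 13 × 8 = 104.
- P(at least one double-dose day) = 1 − (1 − p)^104.
- p = 0.01%: 1 − 0.9999^104 = 1.0%; in 240 participants, about 2.5.
- p = 0.1%: 1 − 0.999^104 = 9.9%; in 240 participants, about 23.7.

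So roughly 2 to 24 participants would have such a day under these assumptions. This is not an estimate for the trial.

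**The case against.** The strongest objection is that the CRF is not among the documents. The SAP was written against a final CRF and names one of its response options. If that form has one row per dosing date, a two-tablet day could be entered only as *other*, and the rule would find it. The authors' use of *i.e.* is consistent with that reading. Footnote 9 does not settle the matter, because it governs the participant's own entry in BYOD, whereas the count uses CRF data, and Section 7.4 provides for reconciliation of BYOD doses. Summing doses for cumulative exposure fits either layout. This objection stands: it makes the missed-pair error conditional, and it rules out saying that such days will certainly be missed or that the rule detects none of them. Nor do the documents say how double doses usually occur or are usually recorded.

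A reader might also infer that this is the only place where an exceeded daily maximum would be seen. It is not. Exposure is listed by participant, protocol 7.4 makes more than one tablet on a calendar day a documented deviation, and SAP 8.2 has a dose-error deviation category that SAP 7.3.2 summarises when the deviation is important. These routes do not replace the count, however. A listing gives no number or percentage. The deviation category covers dose and administration errors generally. A deviation graded minor and not due to COVID-19 would appear only in a listing.

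Finally, a reader might infer that adverse events on double-dose days would fail to be linked to overuse because of this rule. No planned table links adverse events to this flag. SAP 7.5.2 breaks them down by average tablets per month, which does not depend on it.

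**Conclusion.** The point holds as a minor one. SAP 7.5.1 names a calendar-day quantity and defines it by a dose category, without a sum by date and without saying what *other* covers. Whether same-day pairs are missed depends on the CRF layout. Whether unrelated entries are counted depends on the meaning of *other*. Neither is in the documents, so the direction and size of any error are unknown, and the range of 2 to 24 participants only illustrates scale under assumed rates.

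The consequence is limited to one descriptive line. Cumulative dose, average tablets per month and exposure by month are sums of doses and do not use the flag. The deviation and listing routes remain, so the documents do not support the inference that the report as a whole would wrongly show adherence to the daily maximum.

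**What to change.** In SAP 7.5.1, replace the definition based on *other* with a derivation: for each participant and calendar date, sum the tablets over all CRF administration records, then report the number and percentage of participants with any date where the sum exceeds 1, together with the number of such days. Cross-check the flagged participants against the dose-error deviations before database lock and resolve any that appear in only one source.

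If the sponsor prefers to keep the present rule, the SAP should state that the CRF has one row per calendar day and that *other* means more than one tablet.

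The cost is one SAP sentence and a few lines of programming on data already collected. Trial conduct, data collection and the other analyses do not change.
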